7.2.2. Assessment of Severity

The severity grading of AEs will be assessed as Grade 1, 2, 3, or 4 using the GSI Grading Scale for Severity of Adverse Events and Laboratory Abnormalities ([Appendix 3](#)). For AEs associated with laboratory abnormalities, the event should be graded on the basis of the clinical severity in the context of the underlying conditions; this may or may not be in agreement with the grading of the laboratory abnormality.

7.3. Investigator Requirements and Instructions for Reporting Adverse Events and Serious Adverse Events to Gilead

Requirements for collection prior to study drugs initiation:

After informed consent, but prior to initiation of study drugs, the following types of events should be reported on the case report form (eCRF): all SAEs and adverse events related to protocol-mandated procedures.

Adverse Events

Following initiation of study drugs, collect all AEs, regardless of cause or relationship, until 30 days after last administration of study drugs and report to the eCRF database as instructed.

All AEs should be followed up until resolution or until the adverse event is stable, if possible. Gilead Sciences may request that certain AEs be followed beyond the protocol defined follow up period.

Serious Adverse Events

All SAEs, regardless of cause or relationship, that occur after the subject first consents to participate in the study (ie, signing the informed consent) and throughout the duration of the study, including the protocol-required post treatment follow-up period, must be reported to the eCRF database and Gilead Drug Safety and Public Health (DSPH) as instructed. This also includes any SAEs resulting from protocol-associated procedures performed after informed consent is signed.

Investigators are not obligated to actively seek SAEs after the protocol defined follow up period; however, if the investigator learns of any SAEs that occur after study participation has concluded and the event is deemed relevant to the use of study drugs, he/she should promptly document and report the event to Gilead DSPH.

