1.1. Study Objectives

[figure not shown]
The primary objectives of this study are as follows:

- To evaluate the antiviral efficacy of therapy with sofosbuvir/velpatasvir (SOF/VEL) fixed-dose combination (FDC) and ribavirin for 12 or 24 weeks as measured by the proportion of subjects with sustained virologic response 12 weeks after cessation of treatment (SVR12)
- To evaluate the safety and tolerability of each regimen as assessed by review of the accumulated safety data

The secondary objectives of this study are as follows:

- To determine the proportion of subjects who attain SVR at 4 and 24 weeks after cessation of treatment (SVR4 and SVR24)
- To evaluate the proportion of subjects with virologic failure
- To evaluate the kinetics of circulating HCV RNA during treatment and after cessation of each treatment regimen
- To evaluate the emergence of viral resistance to SOF and VEL during treatment and after cessation of treatment

Exploratory objectives of this study are as follows

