4.2.1. Duration of Exposure to Study Drug

Total duration of exposure to study drug will be defined as last dose date – first dose date + 1, regardless of any temporary interruptions in study drug administration, and will be expressed in weeks using up to 1 decimal place (eg, 4.5 weeks).

The total duration of exposure to study drug will be summarized using descriptive statistics (n, mean, SD, median, Q1, Q3, minimum, and maximum) and the number and percentage of subjects (ie, cumulative counts) exposed through the following time periods: baseline (Day 1), Week 1 (Day 7), Week 2 (Day 14), Week 3 (Day 21), Week 4 (Day 28), Week 5 (Day 35), Week 6 (Day 42), Week 8 (Day 56), Week 10 (Day 70), Week 12 (Day 84), and for the 24-week arm only, Week 16 (Day 112), Week 20 (Day 140), and Week 24 (Day 168). A 3-day window will be applied to the last planned on-treatment visit to match with the protocol-specified visit window (ie, the number of subjects exposed through Week 12 or Week 24 will be calculated as the number of subjects who were exposed to study drug for at least 81 days or 165 days, respectively). Summaries will be provided by treatment group for the Safety Analysis Set.

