7.1.5. Treatment-Emergent Adverse Events

7.1.5.1. Definition of Treatment-Emergent

Treatment-emergent adverse events (TEAEs) are defined as one or both of the following:

- Any AEs with an onset date on or after the study drug start date and no later than 30 days after permanent discontinuation of study drug.
- Any AEs leading to premature discontinuation of study drug.

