7.1.6. Summaries of Adverse Events and Deaths

A brief high-level summary of TEAEs will be provided by treatment group and total and by the number and percentage of subjects who had the following: any AE, any AE of Grade 3 or above, any AE of Grade 2 or above, any treatment-related AE, any treatment-related AE of Grade 3 or above, any treatment-related AE of Grade 2 or above, any SAE, any treatment-related SAE, any AE that led to premature discontinuation of any study drug, any AE that led to premature discontinuation of SOF/VEL, any AE that led to premature discontinuation of RBV, any AE that led to premature discontinuation of all study drugs, any AE that led to modification or interruption of any study drug, any AE that led to interruption of SOF/VEL, any AE that led to modification or interruption of RBV, any AE that led to modification or interruption of all study drugs. All deaths (including those that were treatment emergent and those that were not treatment emergent) observed during the study will also be summarized and included in this table.

A brief summary of AEs by age group (ie, <65 years, ≥65 years) and by cirrhosis status will also be explored.

Adverse event summaries will provide the number and percentage of subjects with TEAEs by SOC and PT, by age group, by treatment group and total based on the Safety Analysis Set as follows:

- All AEs
- AEs of Grade 3 or above
- AEs of Grade 2 or above
- All treatment-related AEs

- Treatment-related AEs of Grade 3 or above
- Treatment-related AEs of Grade 2 or above
- All SAEs
- All treatment-related SAEs
- AEs leading to premature discontinuation of any study drug
- AEs leading to premature discontinuation of SOF/VEL
- AEs leading to premature discontinuation of RBV
- AEs leading to premature discontinuation of all study drugs
- AEs leading to modification or interruption of any study drug
- AEs leading to interruption of SOF/VEL
- AEs leading to modification or interruption of RBV
- AEs leading to modification or interruption of all study drugs

Multiple events will be counted once only per subject in each summary. Adverse events will be summarized and listed first in alphabetic order of SOC and then by PT in order of descending incidence in the overall group within each SOC. In summaries by severity grade, the most severe grade will be used for those AEs that occurred more than once in an individual subject during the study.

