7.2.1. Summaries of Numeric Laboratory Results

Descriptive statistics (n, mean, SD, median, Q1, Q3, minimum, and maximum) will be provided by treatment group and total for ALT, aspartate aminotransferase (AST), total bilirubin, alkaline

phosphatase, hemoglobin, reticulocytes, red blood cell (RBC), white blood cell (WBC) counts, neutrophils, lymphocytes, platelets, Albumin, and international normalized ratio (INR) as follows:

- Baseline values
- Values at each postbaseline visit
- Change from baseline at each postbaseline visit

A baseline laboratory value will be defined as the final assessment performed on or prior to the date/time of the first dose of study drug. Change from baseline to a postbaseline visit will be defined as visit value – baseline value. The mean, median, Q1, Q3, minimum, and maximum will be displayed to the reported number of digits, with SD to the reported number of digits plus 1.

The median (Q1, Q3) of the observed values for ALT, AST, total bilirubin, alkaline phosphatase, hemoglobin, reticulocytes, WBC, neutrophils, lymphocytes, and platelets will be plotted using a line plot by treatment group and total and by visit.

In the case of multiple values in an analysis window, data will be selected for analysis as described in Section 3.8.3 (Selection of Data in the Event of Multiple Records in a Window).

The number of subjects with hemoglobin < 10 g/dL and < 8.5 g/dL at any postbaseline visits (up to 30 days after the last dose of any study drug) will be summarized by treatment group and age group and total.

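### Adverse event incidence and low-hemoglobin counts cover 114 planned days in one arm and 198 in the other, and no table splits onset at Week 12

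*SAP*

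**What the plan says.** Safety is one of the two primary objectives (Protocol 2, SAP 1.1): "To evaluate the safety and tolerability of each regimen as assessed by review of the accumulated safety data".

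- **Window.** SAP 7.1.5.1 counts an event as treatment-emergent if it starts on or after the first dose and "no later than 30 days after permanent discontinuation of study drug". Events leading to premature discontinuation also count. Protocol 7.3 sets the same limit on collection: sites "collect all AEs, regardless of cause or relationship, until 30 days after last administration of study drugs". Serious events are collected for the whole study.
- **Adverse event tables.** SAP 7.1.6 gives the overview as "A brief high-level summary of TEAEs will be provided by treatment group and total and by the number and percentage of subjects". For the detailed tables: "Adverse event summaries will provide the number and percentage of subjects with TEAEs by SOC and PT, by age group, by treatment group and total". The counting rule is "Multiple events will be counted once only per subject in each summary".
- **Hemoglobin thresholds.** SAP 7.2.1 plans "The number of subjects with hemoglobin < 10 g/dL and < 8.5 g/dL at any postbaseline visits", up to 30 days after the last dose, by treatment group, age group and total.
- **Hemoglobin by visit.** The same section summarizes the hemoglobin value and its change from baseline at every postbaseline visit, including Q1 and minimum, and plots the median and quartiles by arm and visit. SAP Table 3-1 has separate Week 16, 20 and 24 windows for the 24-week arm.
- **Exposure.** SAP 4.2.1 summarizes treatment duration by arm. No safety table uses it as a denominator.
- **Comparison.** SAP 3.5 plans no comparison between the treatment groups.

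**The concern.** Duration is the only thing randomized, so what Weeks 13 to 24 add in harm is safety information this design is well placed to give. Protocol 1.1.1 says that comorbid conditions in this largely elderly population make ribavirin harder to use, and Protocol 7.5.1 ties ribavirin changes to hemoglobin, with 10 and 8.5 g/dL among the limits.

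A once-per-subject percentage rises with time under observation. If the 24-week column is higher, a reader of the planned adverse event tables cannot tell whether the events arose early, when both arms were treated alike, or late, on the additional treatment. The total column averages a 114-day and a 198-day incidence and describes neither regimen.

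**Working it through.** The plan prints no figure for this point. The window lengths below follow from its own numbers.

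**Inputs**
- Planned treatment: 84 or 168 days (SAP 4.2.1).
- Follow-up for treatment-emergent events: 30 days after the last dose (SAP 7.1.5.1).
- Arm size: 55 each (SAP 1.2).
- Scheduled postbaseline hematology (Protocol Appendix 2): Weeks 1, 2, 3, 4, 5, 6, 8, 10, 12 and posttreatment Week 4. The 24-week arm adds Weeks 16, 20 and 24.
- Event rates: the documents give no expected rates for this trial, so the 12-week values below are assumptions.

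**Windows for a subject who completes treatment**
- 12-week arm: 84 + 30 = 114 days.
- 24-week arm: 168 + 30 = 198 days.
- Ratio: 198/114 = 1.74. Early discontinuation shortens both.
- Hematology visits: 9 + 1 = 10 against 12 + 1 = 13, a ratio of 1.3.

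**What the window alone can do.** With the same constant daily hazard in both arms, p24 = 1 − (1 − p12)^(198/114).

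| Assumed 12-week arm | Implied 24-week arm | Gap in points |
|---|---|---|
| 5% | 8.5% | 3.5 |
| 10% | 16.7% | 6.7 |
| 20% | 32.1% | 12.1 |
| 30% | 46.2% | 16.2 |
| 50% | 70.0% | 20.0 |

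At the other extreme, if every event falls in the shared first 12 weeks, 20% reads as 20% in both arms and the gap is zero.

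**Total column.** In the 20% row with equal arms it would show (20 + 32.1)/2 = 26%, which is neither regimen's incidence.

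**Precision available in the shared period.** Both arms are treated alike to Day 84, so they can be pooled. With the normal-approximation half-width 1.96 × √(p(1 − p)/n) at p = 0.20:
- n = 55: 1.96 × √(0.16/55) = 10.6 points.
- n = 110: 1.96 × √(0.16/110) = 7.5 points.

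**Would one person-time rate do instead?** Full planned windows, not censored at the event, give 55 × 114/365.25 = 17.2 and 55 × 198/365.25 = 29.8 person-years.
- 11/55 against 18/55 (20% against 33%): about 64 against 60 first events per 100 person-years. The rate removes the gap due to longer observation.
- 11/55 in both arms, all early: about 64 against 37. The rate makes the 24-week arm look safer only because its denominator is longer.

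A single rate per arm is therefore informative only if the hazard is roughly constant, which is not known in advance.

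**The case against.** The strongest reply is that the plan does what it sets out to do. The objective concerns each regimen, SAP 3.5 rules out a comparison between arms, and the crude percentage by arm is the burden a patient meets on that regimen. Because the arms are randomized, the crude difference is also a fair estimate of the extra subjects with recorded events under 24 weeks. If the hazard really is constant, more subjects do have events on the longer course, and the table is right to say so. All of this stands.

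A reader might go further and infer three things that the documents do not support.

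- **That safety is reported only as crude percentages.** It is not. SAP 7.2.1, 7.2.2.2 and 7.3 give by-visit summaries of laboratory values, categorical laboratory results and vital signs. The by-visit hemoglobin minimum shows whether any summarized value was below a threshold at Weeks 16, 20 or 24. What it does not show is how many subjects were below it, or how many for the first time.
- **That hemoglobin lows have 1.74 times the chance of detection.** By scheduled visits the ratio is 1.3.
- **That the effect of the extra 12 weeks cannot be recovered.** All adverse events are listed by subject (SAP 3.7 and 7.1.6), so a Week 12 split could be derived for about 110 subjects. But the cut would then be chosen after the data are seen.

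The other side is also right that a late-onset table has no full concurrent comparator. Non-serious events in the 12-week arm stop being collected at about Day 114, so an equal 198-day comparison is possible only for serious events and deaths. The late table must therefore be labelled descriptive. This does not weaken the table for onset through Day 84.

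**Conclusion.** The point holds as a gap in descriptive reporting, not as an error in a planned test. Adverse event incidence and the hemoglobin threshold counts are once-per-subject summaries over 114 versus 198 planned days (10 versus 13 scheduled hematology visits). No table separates onset in the shared 12 weeks from onset afterwards, and the total column pools unequal windows.

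The size depends on timing that the documents do not give. For an assumed 20% in the 12-week arm, the unequal window alone accounts for anything from no gap (all events early) to about 12 points (equal constant hazard). Across assumed rates of 5% to 50%, the constant-hazard gap runs from 3.5 to 20 points. That model treats the 30 days off drug like days on drug, so these figures illustrate the problem and do not predict results. The window lengths assume that planned treatment is completed.

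The crude percentages by arm should stay. The change is worth making because it is cheap, uses dates already collected, and doubles the sample for the period when all subjects are treated alike.

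**What to change.** Amend SAP 7.1.6 and 7.2.1. For the main treatment-emergent categories, adverse events leading to ribavirin modification or interruption, and hemoglobin below 10 and below 8.5 g/dL, add:

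- **(a)** incidence with onset through Day 84, in each arm and pooled (n about 110);
- **(b)** incidence of new onset after Day 84 in the 24-week arm, among subjects still under observation who have not already had that event. Label it descriptive, and note that non-serious events in the 12-week arm are not collected beyond about Day 114, so there is no full concurrent comparator.

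Keep the full-period crude percentages by arm as the burden of each regimen. Show a total column only for Day 1 to 84. A single person-time rate per arm need not be required, because it misleads if events are front-loaded.

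Two conventions are needed. First, SAP 7.1.5.2 handles partial onset dates for treatment emergence but not for a Day 84 cut, so state a rule and footnote how many events it affects. Second, the visit window of ±3 days means a Week 12 blood sample may fall as late as Day 87, so say that the Week 12 visit belongs to the first period for the hemoglobin counts.

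The cost is a few extra tables and these two rules. No new data are needed.

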7.2. Laboratory Evaluations

Laboratory data collected during the study will be analyzed and summarized using both quantitative and qualitative methods. Summaries of laboratory data will be provided for the Safety Analysis Set and will include data collected up to the last dose of study drug plus 30 days for subjects who have permanently discontinued study drug or all available data at the time of the database snapshot for subjects who were ongoing at the time of an interim analysis. The analysis will be based on values reported in conventional units. When values are below the limit of quantitation, they will be listed as such, and the closest imputed value will be used for the purpose of calculating summary statistics. For example, if “< 0.2” was recorded, a value of 0.1 will be used for the purpose of calculating summary statistics; if “< 0.1” was recorded, a value of 0.09 will be used for the purpose of calculating summary statistics. Hemolyzed test results will not be included in the analysis, but they will be listed in by-subject laboratory listings.

A by-subject listing for laboratory test results will be provided by subject ID number and visit in chronological order for hematology, serum chemistry, and urinalysis separately. Values falling outside of the relevant reference range and/or having a severity grade of 1 or higher on the Gilead Grading Scale for Severity of Adverse Events and Laboratory Abnormalities will be flagged in the data listings, as appropriate.

No inferential statistics will be generated.

7.2.1. Summaries of Numeric Laboratory Results

Descriptive statistics (n, mean, SD, median, Q1, Q3, minimum, and maximum) will be provided by treatment group and total for ALT, aspartate aminotransferase (AST), total bilirubin, alkaline

phosphatase, hemoglobin, reticulocytes, red blood cell (RBC), white blood cell (WBC) counts, neutrophils, lymphocytes, platelets, Albumin, and international normalized ratio (INR) as follows:

- Baseline values
- Values at each postbaseline visit
- Change from baseline at each postbaseline visit

A baseline laboratory value will be defined as the final assessment performed on or prior to the date/time of the first dose of study drug. Change from baseline to a postbaseline visit will be defined as visit value – baseline value. The mean, median, Q1, Q3, minimum, and maximum will be displayed to the reported number of digits, with SD to the reported number of digits plus 1.

The median (Q1, Q3) of the observed values for ALT, AST, total bilirubin, alkaline phosphatase, hemoglobin, reticulocytes, WBC, neutrophils, lymphocytes, and platelets will be plotted using a line plot by treatment group and total and by visit.

In the case of multiple values in an analysis window, data will be selected for analysis as described in Section 3.8.3 (Selection of Data in the Event of Multiple Records in a Window).

The number of subjects with hemoglobin < 10 g/dL and < 8.5 g/dL at any postbaseline visits (up to 30 days after the last dose of any study drug) will be summarized by treatment group and age group and total.

7.2.2. Graded Laboratory Values

The Gilead Grading Scale for Severity of Adverse Events and Laboratory Abnormalities will be used for assigning toxicity grades to laboratory results for analysis as Grade 0, Grade 1 (mild), Grade 2 (moderate), Grade 3 (severe), or Grade 4 (potentially life threatening). Grade 0 includes all values that do not meet criteria for an abnormality of at least Grade 1. Some laboratory tests have laboratory toxicity criteria for both increased and decreased levels; analyses for each direction (ie, increased, decreased) will be presented separately.

7.2.2.1. Treatment-Emergent Laboratory Abnormalities

Treatment-emergent laboratory abnormalities are defined as values that increase at least 1 toxicity grade from baseline at any postbaseline time point, up to and including the date of last dose of study drug plus 30 days for subjects who permanently discontinued study drug.

If the relevant baseline laboratory value is missing, then any abnormality of at least Grade 1 will be considered treatment emergent.

7.2.2.2. Summaries of Laboratory Abnormalities

Laboratory data that are categorical will be summarized using the number and percentage of subjects in the study with the given response at baseline and each scheduled postbaseline visit.

The following summaries (number and percentage of subjects) for treatment-emergent laboratory abnormalities will be provided by analyte and treatment group; subjects will be categorized according to the most severe postbaseline abnormality grade for a given analyte:

- Graded laboratory abnormalities
- Grade 3 or above laboratory abnormalities

For all summaries of laboratory abnormalities, the denominator will be the number of subjects with nonmissing postbaseline values up to 30 days after last dose of study drug for the laboratory parameter of interest.

A by-subject listing of treatment-emergent Grade 3 or above laboratory abnormalities will be provided by subject ID number and visit in chronological order. This listing will include all test results that were collected throughout the study for the analyte of interest, with all applicable severity grades or abnormal flags displayed.

7.3. Body Weight, Height, and Vital Signs

Vital signs (systolic and diastolic blood pressure [mmHg], pulse [beats/min]) at each visit and change from baseline at each visit will be summarized for the Safety Analysis Set using descriptive statistics (n, mean, SD, median, Q1, Q3, minimum, and maximum) by treatment group. The baseline value will be defined as the last available value collected on or prior to the date/time of first dose of study drug. Change from baseline to a postbaseline visit will be defined as the postbaseline value minus the baseline value.

In the case of multiple values in an analysis window, data will be selected for analysis as described in Section 3.8.3. No inferential statistics will be generated.

A by-subject listing of vital signs (systolic and diastolic blood pressure [mmHg], pulse [beats/min], respiration [breaths/min], and body temperature [°C]) will be provided by subject ID number and visit in chronological order. In the same manner, a by-subject listing of body weight, height, and BMI will be provided separately.

